#### **F. Study Timeline**

This study will end when the results of an FDA approved clinical trial proves Omegaven® treatment to be ineffective, the product is approved for use in the United States, or funding mechanism no longer exists to supply Omegaven® to study participants.

#### **G. Adverse Event Criteria and Reporting Procedures**

Adverse events (AEs) will be assessed and reported from the time of the first Omegaven® infusion until exit from the study in accordance with UNMC Pediatric IRB reporting requirements. In particular, the patient will be observed during and shortly after Omegaven® administration for the occurrence of anaphylactic or allergic reactions. Other expected adverse events include death, blood stream infection; transfer to ICU for treatment of respiratory distress or hemodynamic instability; re-hospitalization for treatment of blood stream infection, dehydration, electrolyte abnormalities, catheter malfunctions, bowel obstructions, and urinary tract infection. Unexpected adverse events will also be assessed and reported in compliance with the UNMC Pediatric IRB requirements. Patients experiencing any adverse events that are moderate or severe in nature and that may be related to Omegaven® will have their treatment temporarily halted until the adverse event has resolved. Dose modifications will occur as described above. If a dose reduction is made for adverse events later considered to be unrelated to Omegaven®, the Omegaven® dose will be increased back to the dose prescribed prior to the dose reduction. Patients with anaphylactic or allergic reactions will not continue Omegaven® treatment.

Any serious or unsuspected adverse events will be reported to the IRB and the FDA within 72 hours of the occurrence being known, or immediately if the event is fatal or life threatening as per UNMC Pediatric IRB Policy on Adverse and Unexpected Events and Unanticipated Risks to Research Subjects and Others. This will be done in person, by telephone, or email, and by completion of the IRB's form for adverse/unexpected event reporting.

Adverse events are detected by Children's Hospital & Medical Center acute care medical and nursing staff during provision of standard care services including the routine monitoring of vital signs and daily physical exam data. Adverse events identified by Children's Hospital & Medical Center staff are reported to the Principal Investigator immediately by telephone or pager, and subsequently to the appropriate board or committee.

A Committee of the Study Investigators (Drs. [name], [name]) will be responsible for assuring that adverse event reporting requirements are actually met. The Investigator Committee will meet not less than monthly to conduct clinical case reviews of all patients receiving Omegaven® to review recruitment data, adverse events and protocol deviations; and to evaluate overall safety of Omegaven® therapy. Staff dieticians caring for Omegaven® patients will participate in the Investigator meetings as necessary. Any patients who have agreed to participate in the trial,

[name], Department of Surgery, Children's Hospital & Medical Center  
[name], Department of Surgery, Children's Hospital & Medical Center  
[name], Pediatric Research Office, Dept. of Pediatrics, UNMC  
[name], Department of Biostatistics, College of Public Health, UNMC

but who have not yet undergone intervention, will be informed of adverse events. A revised consent document will be submitted to the IRB with the adverse event form for review and approval. All adverse events will be classified by the Principal Investigator as definitely, probably, possibly, or unrelated to administration of study drug.

**Patients will be withdrawn from the study for any of the following:**

- a) Toxicity considered unacceptable by the Principal Investigator (i.e. Evidence of burr cell anemia (reported toxicity); Continued lipid intolerance (triglyceride >200) despite dose reduction attempts and administration modification; evidence of coagulopathy (INR > 2.0)).
- b) Patient/guardian requests to discontinue treatment and/or observation for any reason.
- c) A suitable organ has been located and the patient is able to undergo a liver or liver/intestinal transplant.
- d) Decision by the Principal Investigator that termination is in the patient's best medical interest.
- e) Patient is lost to follow up.

In the event that a patient is withdrawn from the protocol, study staff will document the date of withdrawal, the reason for withdrawal, and the results of all measurements of interest made up to date of withdrawal.

**DATA STORAGE & CONFIDENTIALITY**

This study is being conducted under an FDA Investigational New Drug Application. As such, FDA regulations must be followed. Personal Health Information (PHI) will be protected using standard policies and procedures developed through UNMC according to HIPAA guidelines. Subjects will be assigned specific reference numbers and maintained in a password protected database. The subject's name and medical record number along with the corresponding reference number will be stored in a separate access page. All the research data gathered and stored will be identified by reference number only. The research data will only be accessible to the investigators and data/administrative and healthcare personnel involved in the study. Consent forms and files will be stored in a locked office. Information will not be stored on any personal computer or laptop. The de-identified data will be used for research or regulatory purposes or to prepare research publications. The child's name will never appear in any reports or publications, or in any future disclosures. The child's PHI will be shared, as necessary, with the Institutional Review Board (IRB) and with any person or agency required by law. The research data is subject to disclosure for the duration of the research and until data analysis is complete.

**Retention of Records**

The study coordinator will maintain a comprehensive and centralized filing system of all study related documentation which is suitable for inspection at any time by various regulatory agencies. These include:

- a. Patient files including source documentation and Informed Consent
- b. Study files, including the protocol with all amendments, copies of all regulatory documentation, and all correspondence with the FDA and IRB
- c. Pharmacy files including drug shipment, dispensing, and accountability records, and pharmacy-related correspondence

Per FDA regulations and industry standards, the Primary Investigator will retain records for a period of no less than five (5) years following discontinuation of the study.

[name], Department of Surgery, Children's Hospital & Medical Center  
[name], Department of Surgery, Children's Hospital & Medical Center  
[name], Pediatric Research Office, Dept. of Pediatrics, UNMC  
[name], Department of Biostatistics, College of Public Health, UNMC

## **INFORMED CONSENT**

The Investigator will be responsible for obtaining an Informed Consent signed by each patient or his/her legally authorized representative prior to his/her participation in the study in accordance with the Code of Federal Regulations, Title 21, Part 50.20. Informed Consent will be obtained from a patient or his/her legally authorized representative after a full explanation of the purpose of the study, the risks and discomforts involved, potential benefits, etc. have been provided by the Investigator or designee, both verbally and in writing. The original of the signed consent must be maintained in the patient's research binder; a copy will be maintained in the patient's medical record. The person who signed the consent must also be given a copy of the signed consent form.

## **DATA ANALYSIS PLAN**

Using graphical methods (including boxplots) and descriptive statistics, we will assess assumptions required for validity of statistical methods and presence of outliers. Continuous variables will be summarized via means (and standard deviations) or medians (and interquartile ranges, when appropriate. When appropriate, variables will be transformed.

Primary analyses of the primary outcome will be based on the intention-to-treat analysis i.e., patient will be considered receiving Omegaven® throughout the whole follow-up period, regardless of temporary discontinuation of treatment due to infections or other causes.

### *Analysis of Baseline Characteristics*

For statistical purposes, baseline values will be defined as the last measurement before starting to administer Omegaven®. Descriptive statistics for all baseline relevant risk factors will be summarized using counts and percentages for categorical variables and means (and standard deviations) or medians (and interquartile ranges), when appropriate for continuous variables.

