**Hypothesis for Aim 2:**

2.1 – Our primary hypothesis is that, after reaching bilirubin levels  $> 2$  mg/dL, patients receiving Omegaven® will reach a bilirubin level  $\leq 2$  mg/dL faster than patients receiving conventional fat emulsions. Additionally, while patients receiving Omegaven® will experience a decrease in their levels of bilirubin and other hepatic enzymes over time, patients receiving conventional emulsions will maintain high levels of bilirubin and other hepatic enzymes over time.

2.2 – Patients with surgical gastrointestinal disease and cholestasis will have better clinical hepatic outcomes than patients receiving conventional emulsions.

2.3 – Since patients receiving Omegaven® will have improved immune function, they will have a lower infection rate than patients receiving conventional fat emulsions.

2.4 – Due to a better general hepatic condition, patients receiving Omegaven® will also experience lower occurrence of liver transplant, death from hepatic associated causes, and blood transfusions.

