**Inclusion Criteria:**

1. Patients will be PN dependent (unable to meet nutritional needs solely by enteral nutrition) and are expected to require PN for at least another 30 days.
2. Patients considered eligible for study participation must have parenteral nutrition associated liver disease (PNALD) as defined as a direct bilirubin of  $\geq 2$  mg/dl on at least the last two consecutive measures or by histology and/or currently on Omegaven through another protocol and unable to remain on that protocol due to transfer to our institution. Other causes of liver disease should be excluded. A liver biopsy is not necessary for treatment.
3. The patient must have utilized standard therapies to prevent the progression of his/her liver disease including surgical treatment, cyclic PN, avoiding overfeeding, reduction/removal of copper and manganese from PN, advancement of enteral feeding, and the use of ursodiol (i.e., Actigall®).
4. Patients ages birth up to and including 18 years of age.

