#### Details of Omegaven® Administration

After baseline labs are obtained (Tables 2 and 3), therapy with Omegaven® will be initiated at the goal dose of 1 gram /kg/day and infused over 8-24 hours, so long as the infusion rate does not exceed 0.15g/kg/hour. Omegaven® will be infused intravenously through either a central or peripheral catheter alone or in conjunction with parenteral nutrition. If additional fat calories are needed, they will be provided via the enteral route. The same standards of care provided to all patients receiving parenteral nutrition solution will be followed. Routine nutritional monitoring is described in Table 3.

In the event that a patient is unable to achieve adequate calories parenterally and is unable to tolerate enteral feeds, it may be necessary to evaluate whether or not the patient should continue the study with Omegaven® as monotherapy or resume therapy with conventional fat emulsions so that additional parenteral fat calories can be given. The clinical team, in conjunction with the patient's primary physician, will determine if the patient should be removed from the protocol. The DSMB will also be notified.

Orders for Omegaven® will be entered in Epic and must contain the following data elements:

- Total daily dose to be administered in mL
  - The hourly infusion rate (total daily dose ÷ the number of hours to be infused)
- Prior to the administration of each Omegaven® dose, two nurses will check the dose dispensed against the physician's orders and verify that the infusion pump settings (hourly rate, volume to be infused) are correct before the infusion is started.

As previously mentioned, Omegaven® may be infused in the same manner as conventional fat emulsions through either a central or peripheral line. The emulsion is isotonic. It is compatible with parenteral nutrition solutions and may be co-infused via y-site. Per Infection Control, source containers must be changed every 12 hours and unused product discarded. Omegaven® may be infused through a 1.2micron inline filter.

[name], Department of Surgery, Children's Hospital & Medical Center  
[name], Department of Surgery, Children's Hospital & Medical Center  
[name], Pediatric Research Office, Dept. of Pediatrics, UNMC  
[name], Department of Biostatistics, College of Public Health, UNMC

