### **D. Definition of Primary and Secondary Outcomes/Endpoints**

Generally, primary safety analyses will be based on time from baseline or 30 days after baseline until two months after patients first reached direct bilirubin levels  $< 2$  mg/dL. Baseline will be defined as information collected at the date that treatment starts for Omegaven® patients and on the date that patient reached bilirubin levels  $> 2$  for soybean oil fat emulsion patients. Information on mortality and transplant will be collected during the whole treatment with Omegaven®. Primary efficacy analysis will include time from baseline until the patient normalizes bilirubin (presents three consecutive direct bilirubin  $\leq 2$  mg/dL or a direct bilirubin  $\leq 2$  mg/dL and weaned from TPN).

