#### *Analysis of Efficacy of Omegaven®*

The primary outcome to gain preliminary evidence of efficacy will be based on the time from baseline to normalization of bilirubin level, i.e., first time point among three consecutive in which bilirubin is < 2 mg/dL. We do not anticipate that any subject will present a rebound on direct bilirubin after normalization. However, we will describe the cohort with respect to the frequency of rebounds in bilirubin levels.

Time to normalize direct bilirubin levels will be estimated using Kaplan-Meier curves. We will estimate hazard ratios and adjust for potential baseline confounders using Cox-proportional hazard models. For all survival analysis based on non-parametric or semi-parametric methods, we will attribute an infinite time to event for subjects who die or receive a liver transplant before bilirubin is normalized. Subjects who die before their bilirubin levels normalize (particularly due to liver failure) have in fact the worst outcome (infinite time to normalize bilirubin) and were not censored before reaching the endpoint of interest. Results of these analyses will be compared with results of analysis excluding subjects who die or are transplanted. Time to reach a total bilirubin of 1.2 will also be estimated using survival analysis methods. Analyses of this outcome will proceed as described for direct bilirubin.

We will also describe individual profiles over time (i.e., 2 months before baseline or birth until end of follow-up period) for all subjects using graphical methods. Trends in liver function markers over time will be explored using generalized linear models in which correlations of observations within subjects will be accounted using a generalized equations or random effects approach. We will perform these analyses including only subjects who did not die or undergo transplantation and including all subjects but assigning for subjects who died or underwent a transplant their worse possible outcome after they died or had the transplant. Using descriptive statistics, we will also explore the association between spikes in blood tests over time and predictors including transfusions of red blood cell products and blood stream infections.

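### For children who enter on bilirubin, entry and efficacy success share the 2 mg/dL cut-off and the efficacy analysis names no control, so some stable children near it will normalise by chance

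*Protocol*

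**What the plan says.** **Entry.** Inclusion criterion 2 asks for a direct bilirubin of at least 2 "mg/dl on at least the last two consecutive measures or by histology and/or currently on Omegaven through another protocol". Bilirubin is therefore one of three routes.

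**Baseline.** Under Analysis of Baseline Characteristics, "baseline values will be defined as the last measurement before starting to administer Omegaven". Under Details of Omegaven® Administration, "After baseline labs are obtained (Tables 2 and 3), therapy with Omegaven® will be initiated". Neither passage says whether the baseline draw may be one of the qualifying values.

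**Efficacy event.** Section D counts three consecutive direct bilirubin values at or below 2 mg/dL, or a single such value in a child weaned from PN. Analysis of Efficacy dates the event at the "first time point among three consecutive in which bilirubin is < 2 mg/dL" and leaves out the weaning branch.

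**Comparator.** Hypothesis 2.1 predicts faster normalisation than with conventional emulsions, and that "patients receiving Omegaven® will experience a decrease in their levels of bilirubin and other hepatic enzymes over time". Section D defines a baseline for soybean-oil patients. Analysis of Efficacy mentions hazard ratios and adjustment for confounders but names no comparison group.

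**Earlier values.** "We will also describe individual profiles over time (i.e., 2 months before baseline or birth until end of follow-up period"; this description is graphical. The trend models that follow do not say whether values before baseline are included.

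**The concern.** A child whose true bilirubin is steady a little above 2 mg/dL will, from ordinary fluctuation, sometimes give two values above the cut-off and later three below it. Such a child enters and then counts as a success with no change in the disease. With a concurrent control selected in the same way, this would occur in both groups and largely cancel. Here no control is named in the efficacy analysis, so chance events add to the Kaplan-Meier curve in the direction of the hypothesis.

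The same selection can make mean bilirubin fall after baseline if the baseline is one of the values that qualified the child. At stake is how much of the observed normalisation can be read as preliminary evidence of efficacy.

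**Working it through.** The protocol offers no bilirubin figure to reproduce. Its only power table concerns McNemar tests on adverse events and has no bearing here.

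**Inputs from the protocol.** Entry and event cut-off 2 mg/dL (Inclusion Criteria; section D; Analysis of Efficacy). Weekly bloods while direct bilirubin is at or above 2 mg/dL (lab schedules, Table 3). Illustrative sample sizes of 20, 25 and 30 (Statistical Power and Sample Considerations).

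**Assumptions.** True median bilirubin, spread between children, variation within a child and autocorrelation. The protocol gives none, so ranges are shown. All simulated children are stable: no trend and no drug effect.

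**Step 1: one child at a fixed true level.** Take log-normal fluctuation with within-child CV 40%, so s = √ln(1 + 0.4²) = 0.385, and independent draws. The chance that one value is at or below 2 is p = Φ(ln(2/level)/s). Three given consecutive values all fall at or below 2 with probability p³. Thirteen weekly draws contain 11 such runs, so 11p³ is an upper bound.

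| True level (mg/dL) | p | p³ | Bound 11p³ | Simulated |
|---|---|---|---|---|
| 2.5 | 0.281 | 0.0222 | 24% | 17.5% |
| 3.0 | 0.146 | 0.0031 | 3.4% | 3.0% |
| 4.0 | 0.036 | 0.00005 | 0.05% | about 0.1% (rounded) |

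At 2.0 mg/dL the simulated figure is about 62%, whatever the CV. The effect is local to the cut-off.

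**Step 2: a cohort selected by the entry rule.** Within-child log SD 0.15 to 0.35, autocorrelation 0 to 0.5, 12 weekly values after entry, event = three consecutive values below 2.

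| True median (between-child log SD) | Two-value rule applied once | Entry at first qualifying pair, about 12 weeks scanned |
|---|---|---|
| 3 to 4 mg/dL (0.6) | 1–12% | 4–22% |
| 2 mg/dL (0.4) | 7–31% | 19–47% |

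The protocol permits either pattern of entry. A separate simulation with independent errors (CV 10 to 40%, between-child log SD 0.5, rule applied once, 13 draws, event at or below 2) gave 3.5–16.2% at median 2, 1.5–7.0% at median 3 and 0.3–1.6% at median 5.

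**Step 3: the weaning branch.** In that second simulation at least one value at or below 2 occurred in 20–70% (median 2), 10–50% (median 3) and 3–23% (median 5). These are ceilings, because weaning is also required, but the bilirubin part of this branch gives less protection.

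**Step 4: apparent fall from baseline.** If baseline is the second qualifying value, the geometric mean at the next draw is lower by 0.9–12.3% (median 2), 0.5–7.4% (median 3) or 0.1–2.8% (median 5) with independent errors. If baseline is a fresh draw after the pair, the fall is zero with independent errors; about half of it remains with autocorrelation 0.5.

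**Step 5: candidate remedies, on the Step 2 model.**
- Baseline at or above 4 mg/dL: chance normalisation 0–4% for medians 3 to 5, up to 17% at median 2.
- Also requiring a 50% fall from the pre-treatment mean: 0–6% for medians 3 to 5, up to 12% at median 2.
- Change in slope at Omegaven start, qualifying pair omitted, with first-pair entry: about −0.4% to −6% per week with no drug effect. Over 8 weeks that is 1 − 0.996⁸ = 3% to 1 − 0.94⁸ = 39% of false benefit. Values before a first qualifying pair are selected low, since no earlier pair reached 2.

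**The case against.** The strongest reply is that the endpoint already resists this bias. It is a time to three consecutive values, not a change from one baseline value. Entry takes at least two raised values, an expected further 30 days of PN and prior standard therapies, which points to children with established disease. Step 1 bears this out: at a true 3 mg/dL chance normalisation is at most 3%, and at 4 mg/dL or above it is practically nil. The plan also describes rebounds and separately analyses time to a total bilirubin of 1.2. All of this stands, and it confines the problem to children near the cut-off. It does not remove it, because the protocol sets no higher floor for entry.

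Four stronger readings are tempting, and the documents do not support them.

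- A reader might infer that the baseline is the second qualifying value. The administration and monitoring sections describe bloods drawn before therapy starts, so it may be a fresh draw.
- A reader might infer that every child is selected on bilirubin. Histology and transfer while already on Omegaven are other routes.
- A reader might infer that the earlier values are excluded from modelling. The text confines them to graphs in one sentence but is silent on which time points enter the trend models.
- A reader might conclude that a before-and-after slope contrast should therefore be the efficacy estimate. Step 5 shows that it can create a false benefit of its own.

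The upper figures in Step 2 also need entry at the first qualifying pair. Weekly draws fit inpatients best, because outpatient bloods become monthly below 2 mg/dL.

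**Conclusion.** The point holds for children who enter on bilirubin. One cut-off serves for entry and success, and no control comparison is named, so some stable children near 2 mg/dL will be counted as normalised. Under the stated assumptions this is about 1 to 22% within 12 weekly values at true medians of 3 to 4 mg/dL, more near 2 and close to none well above it. If all 20 to 30 children entered on bilirubin and were stable, that is 0.01 × 20 = 0.2 to 0.22 × 30 = 6.6 apparent successes. The direction is secure; the size depends on variability that the protocol does not give.

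The apparent fall from baseline is a lesser matter, and its presence depends on which draw is the baseline. None of this shows that an observed effect would be an artefact. The plan claims only preliminary evidence of efficacy, so this is an inexpensive improvement to interpretation, not a flaw that defeats the study.

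**What to change.** In Analysis of Efficacy:

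1. Report time to normalisation by baseline direct bilirubin, for example 2 to below 4 and 4 mg/dL or above. Show children who entered by histology or by transfer on Omegaven separately.
2. Add a sensitivity event that requires, besides the existing criterion, a prespecified relative fall (for example 50%) from the mean of the pre-treatment values. Both example thresholds are choices for the sponsor to justify; neither comes from the protocol.
3. State which draw is the baseline. Anchor any change-from-baseline summary on the mean of several pre-treatment values or on a draw separate from the qualifying pair.
4. If slopes before and after the start of Omegaven are modelled, present them as supportive description only, with the caveat that values before a first qualifying pair are selected low and can produce a false change in slope.

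The cost is analysis wording on values the plan already intends to assemble. With about 20 to 30 children the strata will be small, the stricter event will give fewer successes, and newborns or recent transfers may have few earlier values to average.
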